**11.3.3.2. Neonates/Infants**

The infant PPS will include all neonates / infants

- *born to pregnant women in the PPS and*
- *who* meet all eligibility criteria up to the time of their censoring, either at study completion or prematurely as drop-out (e.g. withdrawn consent, lost-to-follow-up) who have at least one time point evaluation (see [Table 5](#)).

**CONFIDENTIAL**207636 (EPI-RSV-008 BOD)  
Protocol Amendment 4 Final**11.4. Derived and transformed data**

Age of the infant subject at time of the LRTI case will be expressed in months and will be computed as the difference between the start date of the LRTI case and the date of birth.

Age of the mother at the time of childbirth will be expressed in years and will be computed as the difference between the birth date of the subject and the birth date of the mother.

Duration of the study for each subject will be computed as the difference between the date of last contact (i.e., active or passive surveillance contact or the date of the censoring) and the date when ICF was first signed by the subject / subject's parent[s]/LAR[s]).

All potential LRTI cases identified during the surveillance period will be classified as RTI, LRTI or severe LRTI according to the LRTI case definition and severity scale (refer to [Table 3](#)). The cases will also be classified according to the classification of WHO [[Modjarrad, 2016](#)].

**11.4.1. Handling of missing values/censoring/discontinuations**

For a given subject and a given demographic variable, missing measurements will not be replaced.

The number of missing values per variable may be provided for selected variables of interest as a separate category. Missing values will be examined to help determine if it is necessary to use multiple imputation or other techniques to deal with missing data.

**11.5. Analysis of demographic and baseline characteristics**

For the maternal PPS cohort, analyses of demographic and baseline characteristics at Visit 1 will be described.

For the infant PPS cohort, analyses of demographic characteristics at Visit 1-NB will be described. Analyses of lifestyle characteristics will be described at Visit 2 NB.

For Screening Failures, reasons for non-eligibility will be described.

*Continuous variables will be summarized by providing the number of observations, mean, 95% confidence interval (CI), standard deviation (SD), median, and range.*

*Categorical variables will be summarized by tabulating counts (N) and the percentage (%) of total subjects having the given characteristics, with missing data considered a separate category.*

**11.6. Analysis of primary objectives (Amended 29 May 2020)**

The primary objectives analyses will be performed on the PPS cohorts overall and possibly by region or other relevant grouping. *If there is a difference of 5% or more between the number of participants in the enrolled set and the PPS, primary objectives analyses on the enrolled set will also be performed.*

**CONFIDENTIAL**207636 (EPI-RSV-008 BOD)  
Protocol Amendment 4 Final**In healthy pregnant women with uncomplicated pregnancies at time of enrollment:**

- To determine the frequencies of pregnancy outcomes.  
The number and percentage (with exact 95% CI) of women presenting the following outcomes: live birth, fetal death/stillbirth (antenpartum or intrapartum), and elective/therapeutic termination will be reported for each event by presence or absence of congenital anomalies.
- To determine the frequencies of pregnancy related events of interest as specified in Section [11.1.1.2](#).  
The number and percentage (with exact 95% CI) of pregnant women presenting with the events of interest specified in Section [11.1.1.2](#) will be tabulated for each event within appropriate time windows to be specified in the statistical analysis plan (SAP). Missing data may be considered a separate category.

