**Number of subjects**

- Approximately 2300 pregnant women. Neonates of enrolled pregnant women who consent to the infant's continued study participation will also be enrolled.

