### **8.2.1. *Study procedures during special circumstances (Amended 29-MAY-2020)***

*During special circumstances (e.g., the COVID-19 pandemic), the specific guidance from local public health and other competent authorities regarding the protection of individuals' welfare must be applied.*

*For the duration of such special circumstances, the following measures may be implemented for enrolled subjects if deemed feasible by the investigator.*

- *If it is not possible to conduct a protocol-specified, scheduled or event-driven (e.g., LRTI assessment) visit as described in Section 8.3, the visit may be replaced with a contact conducted by telephone, videotelephony or telemedicine. SMS and email are not allowed.*
- *Biological samples may be collected at a different location\* other than the study site, or at the subject's home. Biological samples should not be collected if they cannot be obtained within the visit interval (Section 8.4), processed in a timely manner or appropriately stored until the intended use.*
  - *Nasal swabs should only be collected using centrally provided supplies.*
  - *Cord Blood for assessment of immune response may be collected locally but must be retrieved, processed and stored in accordance with the Investigator Laboratory Manual.*
  - *Additional blood samples for assessment of immune response should only be collected using centrally provided supplies.*
- *Diary cards may be transmitted from and to the site by electronic mail, and / or conventional mail.*

*Impact on the per protocol sets for analysis will be determined on a case by case basis.*

*Any impact of the above mentioned measures on the study results will be described in the clinical study report.*

*\* It is the investigator's responsibility to identify an alternate location. The investigator should ensure that this alternate location meets ICH GCP requirements, such as adequate facilities to perform study procedures, appropriate training of the staff and documented delegation of responsibilities in this location. This alternate location should be covered by proper insurance for the conduct of study on participants by investigator and staff at a site other than the designated study site. Refer to EMA Guidance on the Management of Clinical Trials during the COVID-19 (Coronavirus) pandemic (version 2, 27 March, 2020) for more details.*

CONFIDENTIAL

207636 (EPI-RSV-008 BOD)  
Protocol Amendment 4 Final

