### **8.11.1. Use of specified study materials**

When materials are provided by GSK Biologicals, it is MANDATORY that all samples (including serum samples) be collected and stored exclusively using those materials in the appropriate manner. The use of other materials could result in the exclusion of the subject from the per-protocol analysis (See Section [11.3](#) for the definition of study cohorts/data sets to be analyzed). The investigator must ensure that his/her personnel and the laboratory(ies) under his/her supervision comply with this requirement. However, when GSK Biologicals does not provide material for collecting and storing samples, appropriate materials from the investigator's site must be used. Refer to the Module on Clinical Trial Supplies in the SPM.

CONFIDENTIAL

207636 (EPI-RSV-008 BOD)  
Protocol Amendment 4 Final

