## 11. STATISTICAL METHODS

The primary analysis will be performed by country and possibly by region or other relevant grouping if standard of antenatal care is similar in the different sites. This will be determined during site selection when more information is available.

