## 11.2. Determination of sample size

The target will be to enroll up to approximately 200 to 300 eligible subjects (pregnant women) by country. Subjects may drop-out from the study due to a variety of reasons, e.g. migration from the study area. Assuming a drop-out rate of about 10% during the course of follow-up, there will be up to approximately 180 to 270 evaluable subjects by country.

Considering a sample size of up to approximately 180 to 270 evaluable subjects by country, [Table 17](#) illustrates the precision (exact 95% confidence interval [CI]) one can get on the percentage of subjects with maternal, fetal and neonatal events of interest. Precision (exact 95% CI) has also been computed for a sample size of 270, 180 and 100 evaluable subjects for estimate by study site.

The percentages of subjects with maternal, fetal and neonatal events of interest for the primary objectives are expected to range from 0 to 35%.

**Table 17 Precision (exact 95% confidence interval) on the percentage of subjects with maternal, fetal and neonatal events of interest for sample size of 270, 180 and 100 subjects**

% 35 30 25 20 15 10 5 3 1 0	270 subjects			180 subjects			100 subjects		
	N 94.5 81 67.5 54 40.5 27 13.5 8.1 2.7 0	Lower 29.3 24.6 19.9 15.4 11 6.7 2.7 1.3 0.2 0.2 0	Upper 41 35.8 30.6 25.3 19.8 14.2 8.3 5.8 3.1 1.4	N 63 54 45 36 27 18 9 5.4 1.8 0	Lower 28.1 23.4 18.9 14.4 10.1 15.3 2.3 1 0.1 0	Upper 42.4 37.3 32 26.6 21.1 15.3 9.3 6.8 3.9 2	N 35 30 25 20 15 10 5 3 1 0	Lower 25.7 21.2 16.9 12.7 8.6 4.9 1.6 0.6 0 0	Upper 45.2 40 34.7 29.2 23.5 17.6 11.3 8.5 5.4 3.6
		limit limit limit limit limit limit limit limit limit limit limit	limit limit limit limit limit limit limit limit limit limit limit		limit limit limit limit limit limit limit limit limit limit limit				
35	94.5	29.3	41	63	28.1	42.4	35	25.7	45.2
30	81	24.6	35.8	54	23.4	37.3	30	21.2	40
25	67.5	19.9	30.6	45	18.9	32	25	16.9	34.7
20	54	15.4	25.3	36	14.4	26.6	20	12.7	29.2
15	40.5	11	19.8	27	10.1	21.1	15	8.6	23.5
10	27	6.7	14.2	18	6	15.3	10	4.9	17.6
5	13.5	2.7	8.3	9	2.3	9.3	5	1.6	11.3
3	8.1	1.3	5.8	5.4	1	6.8	3	0.6	8.5
1	2.7	0.2	3.1	1.8	0.1	3.9	1	0	5.4
0	0	0	1.4	0	0	2	0	0	3.6

%= Percentage of subjects with maternal, fetal and neonatal events of interest

N= Number of subjects with maternal, fetal and neonatal events of interest

Lower and upper limits are exact 95% confidence intervals

**CONFIDENTIAL**207636 (EPI-RSV-008 BOD)  

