**11.7. Analysis of secondary objectives (Amended 29-MAY-2020)**

The secondary objectives analyses will be performed on the PPS cohorts (maternal or infant as applicable) overall and possibly by region or other relevant grouping. *If there is a difference of 5% or more between the number of participants in the enrolled set and the PPS, secondary objectives analyses on the enrolled set will also be performed.*

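### The Enrolled Set analysis appears only if headcounts differ by 5% or more, so outcome-linked exclusions below that size can shift a rare event's rate unseen; always showing both sets is a cheap improvement

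*Protocol*

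**What the plan says.** Section 11.6 fixes the primary analysis set and level: "The primary objectives analyses will be performed on the PPS cohorts overall and possibly by region or other relevant grouping". It then states the condition for adding the Enrolled Set: "If there is a difference of 5% or more between the number of participants in the enrolled set and the PPS". Section 11.7 has the same condition, after which "secondary objectives analyses on the enrolled set will also be performed". Section 11.8 repeats it for the infant tertiary analyses.

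The rule does not say whether the comparison is made overall, by region or by country, or whether mothers and infants are compared separately. It follows a sentence that says overall, while the opening of Section 11 says: "The primary analysis will be performed by country and possibly by region or other relevant grouping".

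The other provisions that bear on the point are these:

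- **Event frequency.** Section 11.2: "The percentages of subjects with maternal, fetal and neonatal events of interest for the primary objectives are expected to range from 0 to 35" per cent. Table 17 includes rows for 0, 1 and 3%.
- **Maternal PPS (11.3.3.1).** Women in the Enrolled Set who meet the eligibility criteria until they are censored, either at completion or as drop-outs.
- **Infant PPS (11.3.3.2).** The mother must be in the PPS, and the infant must have at least one evaluation.
- **Special circumstances (8.2.1).** "Impact on the per protocol sets for analysis will be determined on a case by case basis". The next sentence requires that any effect of these measures on the results be described in the clinical study report.
- **Screening failures (8.10).** A disqualifying condition that develops after Visit 1 is not a screening failure and is recorded on the eCRF.

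**The concern.** The study exists to supply background rates against which vaccine safety data will be read. Whether exclusions distort such a rate depends on who is excluded, not only on how many. A trigger built on two headcounts cannot tell harmless exclusions from those connected with the outcome.

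The protocol leaves room for such a connection. Gestational hypertension, pre-eclampsia or eclampsia, intrauterine growth restriction, polyhydramnios and oligohydramnios are exclusion criteria in Section 6.3.1, and they correspond to primary events in Section 11.1.1.2. Read literally, a PPS that requires eligibility up to censoring could drop women because they had the event being counted. Among infants, one who dies before any evaluation can be in the Enrolled Set but not in the PPS, although neonatal death is a primary event. The neonatal objective in Section 3.1 concerns all neonates live-born to enrolled women, and the Enrolled Set is closer to that population.

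At stake is transparency. With less than 5% excluded, the report need show only PPS rates, and a reader could not see whether the exclusions moved a rare event.

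**Working it through.** **Inputs.** Enrolment is "Approximately 2300 pregnant women" (synopsis), so N = 2,300. The trigger is 5% (11.6, 11.7). Expected event rates are 0 to 35% (11.2). The protocol gives no expected number of PPS exclusions, so the exclusion scenarios are assumptions.

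**The plan's own figures.** No calculation stands behind the 5% trigger. The precision figures in Table 17 do reproduce: Clopper-Pearson limits agree with all 30 rows within 0.1 percentage point (for example 10% of 270: 6.7 to 14.2).

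**Step 1: largest exclusion that leaves the rule silent.** 5% of 2,300 is 115, so the rule is silent up to k = 114. That is 114/2,300 = 4.96%, and the PPS then holds 2,300 − 114 = 2,186 women. An event at 3% of 2,300 has 69 cases, so silent exclusions can outnumber all cases of an event that rare.

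**Step 2: extreme bounds.** With x events in the PPS, the Enrolled Set rate lies between x/2,300 (no excluded woman is a case) and (x + 114)/2,300 (every excluded woman is a case).

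| PPS rate | x of 2,186 | lower bound | upper bound |
|---|---|---|---|
| 1% | 22 | 22/2,300 = 1.0% | 136/2,300 = 5.9% |
| 3% | 66 | 66/2,300 = 2.9% | 180/2,300 = 7.8% |

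**Step 3: less extreme scenarios.** If excluded women have r times the event risk of those retained, then Enrolled Set rate / PPS rate = (2,186 + 114r)/2,300.

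- r = 2: 2,414/2,300 = 1.05
- r = 5: 2,756/2,300 = 1.20, so 1.0% becomes 1.2% and 3.0% becomes 3.6%
- r = 10: 3,326/2,300 = 1.45

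The exact 95% CI for 22/2,186 is 0.6 to 1.5%, so the five-fold shift from 1.0% to 1.2% stays inside it.

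**Step 4: would a trigger per country cure it?** In a country with 300 women, 5% is 15, so up to 14 exclusions are silent. An event at 3% has 9 cases there, and all 9 could be among the excluded. Narrowing the level of the rule does not solve the rare-event problem.

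**The case against.** The strongest reply is that the two maternal sets may nearly coincide. Deviations from eligibility are not allowed (6.2, 6.3), enrolment requires that all criteria be met (Glossary), drop-outs are censored rather than removed (11.3.3.1), and conditions arising after Visit 1 are not screening failures (8.10). On that reading few women leave the PPS and the effect is small. This stands as a limit on size. It does not settle the matter, because Section 8.10 speaks of screening failure and not of PPS membership, and the wording of 11.3.3.1 permits the literal reading. On the literal reading, exclusions summed over several conditions could also exceed 5% and fire the rule.

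Four stronger inferences are tempting, and the documents do not support them:

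- **That rates may change several-fold.** Overall, this needs excluded women who are almost all cases and an event below about 7%. Moderately outcome-linked exclusion gives the ratios in Step 3.
- **That the rule is pooled over countries, so one country could absorb all 114 exclusions.** The text gives no level. Pooling is inferred from the preceding word overall, and nothing suggests such concentration.
- **That the rule is the only safeguard.** For special circumstances, Section 8.2.1 also requires the impact on results to be described in the study report.
- **That it also fires needlessly over collection materials.** Section 8.11.1 says only that using other materials could lead to exclusion, and 11.3.3 contains no such criterion.

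It is also fair to say that a conditional sensitivity analysis stated in advance is not an error in a descriptive study, and that 11.6 does not forbid the Enrolled Set analysis below the threshold. That is why the point is an improvement and not a fault that invalidates the plan.

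**Conclusion.** The point holds in a limited form. The condition in 11.6 and 11.7 depends on headcounts alone, ignores outcomes and reasons for exclusion, and leaves its level unstated. The plan foresees events below 5% and allows exclusion to be linked to outcome, so a rare event's rate can shift without the Enrolled Set result being shown.

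The size is modest in the scenarios with moderately raised risk: about 1.2-fold at five times the risk among the excluded. The 5.9% and 7.8% figures are outer limits only. All of this assumes 2,300 enrolled, a comparison made overall, and the full 114 exclusions. The effect shrinks if Section 8.10 is taken to keep women with later conditions in the PPS. It is best classed as a cheap improvement.

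**What to change.** In Sections 11.6 and 11.7, delete the 5% condition. State instead that the primary and secondary objectives analyses are always produced on both the Enrolled Set and the PPS, at the same levels (overall and by country), with the number of events among excluded subjects shown beside each event. Section 11.8 can follow if wished.

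The cost is a changed sentence in each section and one extra set of primary and secondary tables. No further data are needed.

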**In all neonates live-born to women enrolled in the study:**

- To determine the frequencies of neonatal events of interest. as specified in Section [11.1.1.3](#).  
The number and percentage (with exact 95% CI) of neonates presenting the events of interest specified in Section [11.1.1.3](#) will be tabulated for each event. Missing data may be considered a separate category.

**11.7. Analysis of secondary objectives (Amended 29-MAY-2020)**

The secondary objectives analyses will be performed on the PPS cohorts (maternal or infant as applicable) overall and possibly by region or other relevant grouping. *If there is a difference of 5% or more between the number of participants in the enrolled set and the PPS, secondary objectives analyses on the enrolled set will also be performed.*

**In healthy pregnant women with uncomplicated pregnancies at time of enrollment:**

- To determine frequencies of pregnancy related events of interest according to GAIA levels of diagnostic certainty (where these are specified) ([APPENDIX D](#))
  - Considering all pregnant women followed from enrollment through Visit 6, the number and percentage of subjects with at least one maternal event of interest will be computed by GAIA levels of diagnostic certainty, with exact 95% CI.
- To describe the distribution of RSV-A antibody titers in maternal blood at delivery.
  - Geometric mean titers (GMTs) will be tabulated with 95% CI.
  - Percentage of subjects above thresholds will be tabulated.

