**CONFIDENTIAL**

207636 (EPI-RSV-008 BOD)  
Protocol Amendment 4 Final

From an analysis perspective, a ‘withdrawal’ from the study refers to any subject who did not come back for the concluding visit in the protocol.

All data collected until the date of withdrawal/last contact of the subject will be used for the analysis.

A subject is considered a ‘withdrawal’ from the study when no study procedure has occurred, no follow-up has been performed and no further information has been collected for this subject from the date of withdrawal/last contact.

Investigators will make at least 3 attempts to contact a subject who does not return for a scheduled visit as described in Section [8.4](#) and in the SPM.

A subject will be defined as lost to follow-up if there is no contact with the subject /subject’s parent(s) / LAR(s) over a period of at least 3 months after a planned visit (see SPM for details). Efforts to contact the subject/subject’s parents should be recorded in the source documents. The subject’s data will be censored at the time of last contact once this definition is met.

Information relevant to the withdrawal will be documented in the eCRF. The investigator will document whether the decision to withdraw a subject from the study was made by the subject herself, by the subject’s parent(s) or LAR(s), or by the investigator, as well as which of the following possible reasons was responsible for withdrawal:

- Study participation related SAE.
- Pregnancy related event of interest(specify). Note: includes maternal deaths.
- Maternal deaths not related to pregnancy/delivery (specify cause).
- Neonatal event of interest(specify). Note: includes death in infants from birth – 28 days old
- Death in infants > 28 days old (specify cause). Note that death in neonates from birth – 28 days old is captured as a neonatal event of interest).
- Protocol violation (specify).
- Consent withdrawal\*.
- Moved from the study area.
- Lost to follow-up.
- Other (specify).

\*In case a subject is withdrawn from the study because she/the subject’s parent(s)/ LAR(s) has withdrawn consent, the investigator will document the reason for withdrawal of consent, if specified by the subject/ the subject’s parent(s)/LAR(s), in the CRF.

Subjects who are withdrawn from the study because of study participation related SAEs must be clearly distinguished from subjects who are withdrawn for other reasons.

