**11.3.3. Per Protocol Sets (PPS) (Amended 29-MAY-2020)****11.3.3.1. Pregnant women (mothers)**

The maternal PPS will include all pregnant women (mothers) *in the enrolled set who* meet all eligibility criteria up to the time of their censoring, either at study completion or prematurely as drop-out (e.g. withdrawn consent, lost-to-follow-up).

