**In all neonates/infants live-born to women enrolled in the study:**

- To determine the incidence of all, of severe, and of very severe RSV-lower respiratory tract illnesses (LRTIs).
  - Considering all infants followed from visit 1-NB to visit 4-NB, the percentage of subjects with at least one LRTI illness, exact 95% CI will be presented.
  - Incidence rates of LRTI illnesses will be calculated, with exact 95% CI.
  - Frequencies of repeat occurrences of LRTI will be tabulated.
- To determine the incidence of RSV hospitalization.
  - Considering all infants followed from visit 1-NB to visit 4-NB, the percentage of subjects with at least one RSV hospitalization, with exact 95% CI.
  - Incidence rates of RSV hospitalizations will be calculated, with exact 95% CI.
  - Frequencies of repeat occurrences of RSV hospitalization will be tabulated.

Continuous variables will be summarized by providing the number of observations, mean, 95% CI, SD, median, and range. Categorical variables will be summarized by tabulating N and % of total subjects having the given characteristics, with missing data considered a separate category.

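### Secondary percentages in 11.7 (and co-infections in 11.8) are worded for completers only, against 10.2 and the per-protocol set definition; maternal death by GAIA level becomes zero by construction

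*Protocol*

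**What the plan says.** Section 11.7 gives three percentages with a follow-up condition attached:

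- Maternal events by GAIA level: "Considering all pregnant women followed from enrollment through Visit 6, the number and percentage of subjects with at least one maternal event of interest".
- RSV-LRTI: "Considering all infants followed from visit 1-NB to visit 4-NB, the percentage of subjects with at least one LRTI illness".
- RSV hospitalization: "Considering all infants followed from visit 1-NB to visit 4-NB, the percentage of subjects with at least one RSV hospitalization".

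The co-infection percentage in Section 11.8 repeats the infant wording. Visit 6 and Visit 4-NB are the concluding visits (Tables 5 and 6), and Section 10.1 counts as a completer anyone who returns for the concluding visit.

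Two other places say something different. Section 10.2: "All data collected until the date of withdrawal/last contact of the subject will be used for the analysis". Section 11.3.3 defines the maternal per-protocol set, which 11.7 names for these analyses, as enrolled women who "meet all eligibility criteria up to the time of their censoring, either at study completion or prematurely as drop-out"; the infant set is defined the same way. Section 10.2 treats anyone who misses the concluding visit as a withdrawal for analysis purposes. Its withdrawal reasons include "Pregnancy related event of interest(specify). Note: includes maternal deaths" and, separately, infant death after 28 days.

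**The concern.** The protocol gives two incompatible denominators for the same tables. One is the set of subjects observed to the last visit. The other is a per-protocol set that keeps people who left early. Two analysts working from this text could report different percentages and both claim to have followed it.

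The literal version has a specific defect. Maternal death is a listed event of interest with its own GAIA levels in Appendix D, and a woman who dies before Visit 6 cannot have been followed through it. Likewise an infant who dies, or whose family leaves, after an RSV episode is removed together with that episode. Section 1.1 says that the RSV incidence estimates are meant to support event-rate assumptions for later efficacy trials, so a systematic understatement would carry forward.

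**Working it through.** **The wording side by side.**

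- Completer reading of 11.7: the denominator is those with the concluding visit, so deaths and withdrawals are out.
- Section 10.2: their data up to last contact are used.
- Section 11.3.3: they belong to the named analysis set.
- The neonatal GAIA item, next to these in 11.7, refers to all neonates with no follow-up condition. The condition elsewhere therefore looks deliberate.

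**The plan's own figures (Section 11.2).** About 10% drop-out: 200 × 0.9 = 180 and 300 × 0.9 = 270 evaluable per country, as stated. Table 17 for 10% of 270 gives 6.7 to 14.2; the exact (Clopper-Pearson) limits for 27/270 are 6.69 and 14.22. Both agree.

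**Maternal death under the completer wording.** For a death inside the Visit 1 to Visit 6 window, the numerator is 0 whatever the true risk. With 2300 × 0.9 = 2070 completers, the table would show 0/2070, with exact upper limit 1 − 0.025^(1/2070) = 0.18%. The documents give no death risk. Over an assumed range of 0.1% to 1%, the expected number in 2300 women is 2.3 to 23.

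**Infant RSV, completer wording.** Let true 12-month risk be p = 10%, overall non-completion 10%, and non-completion k times as likely after an event. Then q0 = 0.10/(1 − p + kp), q1 = k·q0, and the completer percentage is p(1 − q1)/0.90.

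| k (assumed) | q1 | Completer percentage |
|---|---|---|
| 1 | 0.100 | 10.0% |
| 2 | 0.182 | 9.1% |
| 3 | 0.250 | 8.3% |
| 5 | 0.357 | 7.1% |

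So there is no bias when loss is unrelated to the event, and a downward one when it is related.

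**Infant RSV, whole per-protocol set, crude percentage.** Constant hazard h = −ln(1 − p) = 0.1054, with 10% lost independently of events.

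- Loss spread evenly over the year: mean risk observed in those lost = 1 − p/h = 1 − 0.10/0.1054 = 0.051. Crude percentage = 0.9 × 0.10 + 0.1 × 0.051 = 9.5%, a relative −5%.
- All loss at the start: 0.9 × 0.10 = 9.0%, a relative −10%.
- The same calculation for a true 20% gives 19.0% and 18.0%.

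**Censored estimate.** In a simulation of the even-loss case, an estimate based on time at risk up to last contact returned 10.0% and 20.0% for true risks of 10% and 20%. The crude percentages were 9.5% and 19.1%.

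**Scale.** The shift of 0.5 to 1.0 point is small beside one country's interval (6.7 to 14.2). It is not negligible beside the overall analysis, where 1.96 × √(0.10 × 0.90/2070) ≈ 1.3 points.

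**The case against.** The strongest reply is that the phrases describe the surveillance window rather than an exclusion. The objectives use the same Visit 1 to Visit 6 span, the analysis set is named separately, and nothing says that withdrawn subjects are removed from these tables. That reading is reasonable, and may be what was intended. It does not remove the conflict, because the text restricts who is considered, and it leaves open how partial follow-up enters a 12-month percentage.

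It is also fair that the protocol already holds partial remedies. Section 11.7 plans RSV incidence rates with exact intervals and a missing category, and Section 11.4.1 leaves imputation open. The incidence rates do help for infants, but the percentages beside them stay as worded and the maternal GAIA items have no such companion. A missing category helps little for event-driven endpoints: an infant lost at month 4 may simply have no event record.

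A reader might go further and infer three things that the documents do not support.

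- That maternal death cannot be counted in this study. It can: it is a primary endpoint, and 11.6 tabulates it on the per-protocol set without any completer condition.
- That event percentages in general are affected. The wording is confined to three items in 11.7 and one in 11.8; the primary and neonatal percentages do not carry it.
- That women with non-fatal events are systematically withdrawn. Section 10.2 only lists reasons to record, and 8.5.8 keeps following women even when there is no live birth.

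**Conclusion.** The point stands in a limited form. The denominators of the maternal GAIA-level percentages, the two infant RSV percentages and the co-infection percentage contradict Section 10.2 and the per-protocol set definition. The certain consequence of the literal wording is a GAIA-level maternal death result fixed at 0, together with the loss of RSV events in infants who later die or withdraw. The size for RSV is conditional. At a true risk of 10%, completers-only gives 7.1% to 9.1% if non-completion is 2 to 5 times as likely after an event, and is unbiased if loss is unrelated. The crude per-protocol percentage gives 9.0% to 9.5% at the planned 10% loss. The 10% loss is the protocol's; the 10% risk, the constant hazard, the ratios and the death risks are assumptions.

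The study is descriptive and only secondary and tertiary tables are touched. Nothing here calls for moving the primary analysis to the Enrolled Set, or for time-to-event methods for pregnancy events in 11.6; those are matters of preference or for the SAP.

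**What to change.** In the maternal GAIA item and the two infant RSV items of 11.7, and in the co-infection item of 11.8, replace the follow-up condition with all subjects in the named analysis set. State that every event up to last contact counts, death included.

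For infant RSV-LRTI and RSV hospitalization, report cumulative incidence to 12 months with censoring at last contact and death as a competing event, next to the incidence rates already planned. Keep the completer percentage as a supportive line only.

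The cost is a few lines of protocol text and a little extra programming. Section 11.4 already uses birth date, LRTI start date and date of last contact, and 10.2 records death as a withdrawal reason. That the eCRF holds dates of death and of hospital admission should be confirmed, since the protocol does not name them.
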